3.4.2. Exclusion Criteria

Participants meeting ANY of the following criteria at time of Screening will be excluded from enrollment:

1. The participant has a known history of, or a positive test result for, hepatitis B surface antigen (HBsAg), hepatitis C virus (HCV), or human immunodeficiency virus (HIV) at screening.
2. As reported by the participant has severe cardiovascular disease, neurological disease, hematological disease, infectious disease, mental disorder, liver disease, gastrointestinal disease, lung disease, endocrine disease, immune disease or kidney disease, or has a history of the above diseases, or other symptoms known to interfere with the absorption, distribution, metabolism, or excretion of the medicine, or other conditions that the Investigator believes will increase the risk of the participant and might interfere with the study conduct and results interpretation.
3. The participant has history or presence of active lung disease (i.e., asthma, chronic obstructive pulmonary disease [COPD], pulmonary fibrosis, hemoptysis, bronchiectasis) or prior intubation due to respiratory failure conditions.
4. The participant has upper respiratory infection within the 3 months prior to the first dose of study drug.
5. Consumed more than 14 units of alcohol per week in the 6 months before screening (1 unit of alcohol = 360 mL of beer or 45 mL of spirits with 40% alcohol content or 150 mL of wine) or have taken alcohol products in the 48 hours prior to administration, or those who have a positive alcohol breath test result at screening and day -1.
6. Unwillingness to abstain from the consumption of any caffeine or alcohol-containing food or drinks that may influence the drug metabolism from 48 hours before administration.

7. History of drug abuse or a positive drug abuse (barbiturates, methamphetamine, benzodiazepines, morphine/opiates, phencyclidine (PCP), amphetamines, tetrahydrocannabinol (THC), methylenedioxymethamphetamine (MDMA), cocaine, methadone, and cotinine) test result at screening and day -1.
8. Female participants who are lactating.
9. Use of prescription or non-prescription drugs, including vaccine within 14 days or 5 half-lives (whichever is longer) prior to the first dose of study drug.
10. The participant has received an experimental agent (vaccine, drug, biologic, device, blood product or medication) within 1 month prior to the first dose of study drug and will receive another experimental agent during the duration of this study.

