11. The participant has a history of frequent nose bleeding.
12. Participants with known allergic reactions to the study drug or its excipients.
13. The participant has an acute sinusitis or history of chronic sinusitis, a history of active allergic rhinitis (AR), history of perennial allergic rhinitis (PAR), or current seasonal allergic rhinitis (SAR), or recent viral rhinitis within 2 weeks prior to administration.
14. The participant has Any nasopharyngeal abnormality that may have interfered with nasal absorption, distribution, or study-related evaluations of signs or symptoms (e.g., polyps, septal deviation).
15. Blood donation of more than 400 mL within 3 months before screening or more than 200 mL within 4 weeks before screening or plan to donate blood during study period.
16. Any other clinical condition that, in the Investigator's judgment, would potentially compromise study compliance or the ability to evaluate safety/efficacy.

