6.2. CONCOMITANT MEDICATIONS

Unless medication is necessary for safety reasons and approved by the Sponsor and the Investigator, participants must abstain from taking any prescription or non-prescription drugs, within 14 days or 5 times the half-life (whichever is longer) prior to the first dose of IP until completion of the study.

During the entire study period, participants must adhere to the following prohibitions:

- Able to abstain from the use of nicotine/tobacco containing products during the study.
- Able to abstain from the consumption of alcohol and any alcohol-containing products from 48 hours before dosing to the end of the study.
- Able to abstain from the consumption of coffee and any caffeine-containing products from 48 hours before dosing to the end of study.

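### Exclusion 10 joins prior and on-study use of an experimental agent with *and*, so under it neither alone excludes, and other rules only partly fill the gap

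*Protocol*

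**What the plan says.** Protocol section 3.4.2, Exclusion 10, describes a participant who has received an experimental agent (the listed types include vaccine, drug, biologic, device and blood product) "within 1 month prior to the first dose of study drug and will receive another experimental agent during the duration of this study". The synopsis repeats the criterion with the same connective. The list opens with "Participants meeting ANY of the following criteria at time of Screening will be excluded from enrollment".

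Five other provisions bear on the point:

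- Exclusion 9 covers "Use of prescription or non-prescription drugs, including vaccine within 14 days or 5 half-lives (whichever is longer") before the first dose. It does not name experimental agents, devices or blood products.
- Section 6.2 asks participants to stay off such drugs from the same pre-dose window until they complete the study, with an exception for medication needed for safety and approved by the Sponsor and Investigator.
- Inclusion 9 requires willingness to follow the whole protocol.
- Exclusion 15, which also combines past and planned behaviour, ends with "or plan to donate blood during study period".
- Exclusion 16 covers "Any other clinical condition that, in the Investigator's judgment, would potentially compromise study compliance" or the evaluation of safety or efficacy.

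The SAP does not restate the eligibility criteria.

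**The concern.** A criterion of this kind normally serves two separate purposes: to keep out people recently exposed to another investigational product, and to keep out people who will be exposed to one during the trial. Joined by *and*, it does neither on its own.

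Safety and tolerability are the primary objective (section 2.1.1) of a first-in-human study (section 1.4.2). The escalation criteria in section 3.1 turn on very few related events: one related SAE, one participant with a related Grade 4 event, or two participants with related Grade 3 events. Exposure to another investigational agent could blur the relatedness judgment on which each of these depends.

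The wording also switches off a safeguard. Section 11.4.1 lists enrolling an ineligible person without sponsor approval as a major deviation. Someone who meets only one half of Exclusion 10 is eligible as written, so their enrolment is not flagged on that ground.

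**Working it through.** The plan gives no figure here, so the check is one of logic followed by coverage.

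**Step 1: what Exclusion 10 does.** Let P be receipt of an experimental agent in the month before first dose, and F be receipt of another during the study.

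| P | F | As written (P and F) | With *or* (P or F) |
|---|---|---|---|
| yes | yes | excluded | excluded |
| yes | no | not excluded | excluded |
| no | yes | not excluded | excluded |
| no | no | not excluded | not excluded |

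As written, 1 of 4 combinations is excluded; with *or*, 3 of 4. The lead-in to the list says that any one numbered criterion is enough. It works between items and does not split item 10 into two.

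**Step 2: what was probably meant.** Exclusion 15 has the same past-plus-planned structure and uses *or*. Read literally, Exclusion 10 would hardly ever apply. That either half was meant to exclude alone is an inference, but a strong one.

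**Step 3: prior use only (P without F).** Assume that Exclusion 9 reaches investigational drugs and vaccines, and take one month as 30 days. With half-life h in days, Exclusion 9 covers max(14, 5h) days, so the uncovered part is 30 − max(14, 5h), or zero if that is negative.

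- 5h at or below 14 (h up to 14/5 = 2.8 days): 30 − 14 = 16 days, about Day -30 to Day -15.
- h = 4.2 days: 5 × 4.2 = 21, leaving 30 − 21 = 9 days.
- h = 6 days or more: 5 × 6 = 30, leaving nothing.

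The gap is therefore at its full width for agents whose five half-lives fit within 14 days, and shrinks to nothing as the half-life approaches 6 days. Experimental devices and blood products are not named in Exclusion 9, so for them the whole month is open.

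**Step 4: planned use only (F without P).** Section 6.2 is a conduct rule, not an eligibility criterion. But a person who intends to take another trial's drug would be hard to reconcile with Inclusion 9, so planned drugs are arguably barred at entry. Section 6.2 speaks only of drugs, so planned experimental devices and blood products are not reached.

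**Step 5: catch-alls.** Exclusion 16 is confined to a clinical condition. The other-conditions clause of Exclusion 2 depends on what the Investigator believes. Neither states that prior or planned experimental use alone excludes.

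**The case against.** The best case for the plan is that little gets through, and that what does is mostly harmless.

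- **Coverage.** A reader might infer that anyone dosed in another trial three weeks earlier passes. The documents do not support that in general: if Exclusion 9 reaches investigational drugs, one with a half-life above 21/5 = 4.2 days is still excluded at three weeks. A reader might also infer that anyone planning to join another drug trial during follow-up passes. Section 6.2 with Inclusion 9 arguably stops that, and taking a prohibited medication is a listed major deviation. Both points stand and limit the gap.
- **Carry-over.** A drug that clears Exclusion 9 is at least five half-lives past dosing, so under first-order elimination no more than 0.5^5 = 3.1% remains. This stands for plasma levels. It does not speak to effects that outlast the drug, or to devices and blood products.
- **Detection.** Section 7.7 records medications and therapies from 14 days before Screening, section 9.2.3 weighs other therapies in judging causality, and each cohort has two placebo participants. So the most that can be said is that events *could* be misattributed to MBS-COV, not that they would be. Detection is incomplete, though: recording reaches back 30 days only if Screening falls on or before about Day -16 (30 − 14 = 16).
- **Wording.** The word *another* may simply mean an agent other than MBS-COV, and a sensible site may apply the evident intent. That is fair, but both statements of the criterion carry the same *and*, so neither corrects the other.

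**Conclusion.** Exclusion 10 is wrong as written: under it, neither prior-month use nor on-study use of an experimental agent excludes by itself. After allowing for the other provisions, what remains open is:

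- prior experimental drugs or vaccines whose five half-lives are under 14 days, taken from about Day -30 to Day -15, roughly 16 of 30 days; and
- experimental devices or blood products, whether prior or planned.

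This rests on three assumptions: a month of 30 days, Exclusion 9 and section 6.2 applying to investigational drugs, and Inclusion 9 being applied to stated plans. If investigational drugs do not count as prescription or non-prescription drugs, the gap is wider.

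The consequence is possible confounding of causality and of the escalation criteria, without an eligibility deviation to mark it. Its frequency cannot be estimated from the documents. It may be tempting to note that one participant is 1/6 (16.7%) of an active arm in Part A or 1/8 (12.5%) in Part B. Those are arm sizes, not a measure of impact: they assume that such a person enrols and is randomized to active treatment. This is a drafting error in an operative eligibility rule. It does not touch the sample size of 44, which is not based on power.

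**What to change.** In Exclusion 10, replace *and will receive* with *or will receive*, in section 3.4.2 and in the synopsis together. This makes each half exclude on its own, covers all the listed types of agent, and makes enrolment against either half an eligibility deviation.

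The cost is one word in two places at the next amendment. It adds no procedure and changes nothing in dosing or analysis. The only downside is a marginally smaller screening pool.

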4. STUDY SCHEDULE

4.1. OVERVIEW

The study Schedule of Assessments in presented in [Table 4-1](#) (Part A) and Table 4-2 (Part B). See [Section 7](#) for a detailed description of each protocol assessment and procedure.

The study is divided into three phases: Screening Phase, Treatment Phase, and Follow-Up Phase.

Table 4-1: Schedule of Assessments – Part A (SAD Phase)

Procedure/Assessments	Screening Phase	Treatment Phase							Follow-Up Phase			
		Inpatient Visit				Outpatient Visits						
		Visit	SV	T0	T1 (Baseline)		T2	T3	T4	T5 (EOT/ET)	FU1	FU2 ^[19]
					(Pre-Rx)	(Post-Rx)						
Day	Up to -28	Day -1		Day 1			Day 2	Day 3 (48 hours after dosing)	Day 4	Day 7	Day 14	Day 28
Window Period				Within 28 days of the Screening Visit			NA	NA	NA	±1	±1	±1
ASSESSMENTS												
Informed Consent ^[1]	X											
Eligibility Evaluation ^[2]	X	X										
Participant Demographics	X											
Medical History ^[3]	X	X	X									
Physical Examination	X		X	X ^[4]	X ^[4]	X ^[4]	X ^[4]	X ^[4]	X ^[4]	X		
Height, Weight and BMI	X											
Vital Signs	X	X	X	X ^[5]	X	X	X	X	X	X		
12-lead ECG	X	X	X	X ^[6]	X	X	X	X	X	X		
Chest X-ray	X								X			
Spirometry assessments ^[7]	X	X		X								
Participant Confined to Research Clinic		X	X	X	X							
Participant Discharge from Research Clinic (if applicable) ^[8]							X					
Randomization			X									
Concomitant Medications	X	X	X	X	X	X	X	X	X	X		
Adverse Events				X	X	X	X	X	X	X		
LABORATORY TESTS^[9]:												
Hematology ^[10]	X	X			X	X			X	X		
Biochemistry ^[11]	X	X			X	X			X	X		
Coagulation Indices ^[12]	X	X			X	X			X	X		
Serum/Urine Pregnancy Test ^[13]	X	X							X	X		
Urinalysis ^[14]	X	X			X	X			X	X		

Procedure/Assessments	Screening Phase	Treatment Phase								Follow-Up Phase			
		Inpatient Visit				Outpatient Visits							
		Visit	SV	T0	T1 (Baseline)		T2	T3	T4	T5 (EOT/ET)	FU1	FU2 ^[19]	
					(Pre-Rx)	(Post-Rx)							
Day	Up to -28	Day -1	Day 1		Day 2	Day 3 (48 hours after dosing)	Day 4	Day 7	Day 14	Day 28			
Window Period			Within 28 days of the Screening Visit		NA	NA	NA	±1	±1	±1			
Nasopharyngeal or nasal swab for COVID-19 ^[15]	X	X				X	X	X	X	X			
Urine Drug and Alcohol Screening	X	X											
PK evaluations ^[16]			X	X	X	X							
ADA ^[17]			X							X	X		
Screening for infectious diseases (HIV antibody; HbsAg; HCV antibody)	X												
INTERVENTION(s):													
MBS-COV Administration ^[18]			X										

- [1] Informed consent must be obtained prior to participation in any protocol-related activities that are not part of routine care.
- [2] Initial evaluation of participant eligibility will be performed by Investigator.
- [3] Medical history and current therapies (medications and non-medications).
- [4] Symptom-directed physical examination.
- [5] Vital signs will include blood pressure, pulse, respiration rate, and temperature. On treatment visits will be conducted three times a day, within 120 minutes before administration, within 1 hour after administration, and 4-6 hours after administration, respectively. On other visits will be conducted once during the visit.
- [6] 12-lead ECG on treatment visits will be conducted three times a day, within 120 minutes before administration, within 1 hour after administration, and 4-6 hours after administration, respectively. On other visits will be conducted once during the visit.
- [7] Spirometry assessments will be started 5 minutes after the dosing with frequent spirometry measurements at 5 (± 1 min), 15 (± 1 min), 30 (± 5 min), 60 minutes (± 5 min). On other visits will be conducted once during the visit. If spirometry is completed within 7 days prior to dosing, this assessment does not need to be repeated on Day-1.
- [8] Participants will be discharge from the clinic when all required assessments for T3 Day (3) are performed.
- [9] If hematology, biochemistry, coagulation and urinalysis are completed within 7 days prior to dosing, this assessment does not need to be repeated on Day-1.
- [10] Hematology
Hemoglobin, Hematocrit (HCT), Red Blood Cells (RBC), White Blood Cells (WBC) with total and differential count, Absolute Neutrophil Count (ANC) and platelets.
- [11] Biochemistry
Hepatic function indicators: total bilirubin, alkaline phosphatase, aspartate aminotransferase (AST), alanine aminotransferase (ALT), total protein, albumin, Lactate dehydrogenase (LDH), amylase and lipase

Renal function indicators: Serum creatinine, eGFR

Electrolytes: sodium, potassium, chloride, calcium and bicarbonate

Other: glucose (random), triglyceride (TG), cholesterol (total), Creatine kinase.

[12] Coagulation

Prothrombin time (PT), activated partial thromboplastin time (APTT), thrombin time (TT), fibrinogen (FIB)

[13] Serum pregnancy test in screening visit (Will include FSH and estradiol levels at screening for post-menopausal women only) and EOT, and Urine pregnancy test in other visits.

[14] Urine samples will be tested for color, appearance, specific gravity, pH, protein, glucose, occult blood, ketones, leukocyte esterase, nitrite, bilirubin, and urobilinogen.

[15] Nasopharyngeal or nasal swab sample will be collected for COVID-19 antigen rapid test at screening and qRT-PCR test on Day -1, Day 3, Day 4, Day 7, Day 14 and Day 28.

[16] PK timepoints: Cohorts A1 to A3: For the single dose on day 1, blood samples will be collected before dosing, and afterwards at 5 min (\pm 1 min), 15 min (\pm 2 min), 0.5h (\pm 5 min), 1h (\pm 5 min), 2h (\pm 5 min), 4h (\pm 5 min), 8h (\pm 10 min), 10 h (\pm 10 min), 24 h (\pm 10 min) and 48 h (\pm 10 min) after dosing.

[17] ADA timepoints: Blood samples will be collected on Day 1 before dosing, Day 14, and Day 28.

[18] IP administration: SAD cohorts A1-A3: Single MBS-COV treatment administration through a portable nebulizer (0.3 - 1.2 mg/kg).

[19] Adverse events and concomitant medications will be followed up on Day 28.

Table 4-2: Schedule of Assessments – Part B (MAD Phase)

Procedure/Assessments	Screening Phase	Treatment Phase						Follow-Up Phase			
		Inpatient Visits									
Visit	SV	T0	T1 (Baseline)		T2-T7	T8	T9(EOT/ET)	FU1	FU2 ^[19]		
			(Pre-Rx)	(Post-Rx)							
Day	Up to -28	Day -1	Day 1		Day 2-Day 7		Day 8	Day 9 (48 hours after last dosing)	Day 14	Day 28	
Window Period			Within 28 days of the Screening Visit		NA		NA	±1	±1	±1	
ASSESSMENTS											
Informed Consent ^[1]	X										
Eligibility Evaluation ^[2]	X	X									
Participant Demographics	X										
Medical History ^[3]	X	X	X								
Physical Examination	X		X	X ^[4]		X ^[4]	X ^[4]	X ^[4]	X		
Height, Weight and BMI	X										
Vital Signs	X	X	X	X ^[5]		X ^[5]	X	X	X		
12-lead ECG	X	X	X	X ^[6]		X ^[6]	X	X	X		
Chest X-ray	X							X			
Spirometry assessments ^[7]	X	X		X		X					
Participant Confined to Research Clinic		X	X			X	X				
Participant Discharge from research clinic (if applicable) ^[8]								X			
Randomization			X								
Concomitant Medications	X	X	X	X		X	X	X	X		
Adverse Events				X		X	X	X	X		
LABORATORY ASSESSMENTS^[9]											
Hematology ^[10]	X	X			X	X	X	X			
Biochemistry ^[11]	X	X			X	X	X	X			
Coagulation Indices ^[12]	X	X			X	X	X	X			
Serum/Urine Pregnancy Test ^[13]	X	X					X	X			

Procedure/Assessments	Screening Phase	Treatment Phase						Follow-Up Phase	
		Inpatient Visits							
Visit	SV	T0	T1 (Baseline)		T2-T7	T8	T9(EOT/ET)	FU1	FU2 ^[19]
Day	Up to -28	Day -1	Day 1		Day 2-Day 7	Day 8	Day 9 (48 hours after last dosing)	Day 14	Day 28
Window Period			Within 28 days of the Screening Visit		NA	NA	±1	±1	±1
Urinalysis ^[14]	X	X			X	X	X	X	
Nasopharyngeal or Nasal Swab for COVID-19 ^[15]	X	X					X	X	X
Urine Drug and Alcohol Screening	X	X							
PK evaluations ^[16]			X	X	X	X	X		
ADA ^[17]			X					X	X
Screening for infectious diseases (HIV antibody; HbsAg; HCV antibody)	X								
INTERVENTION(s)									
MBS-COV Administration ^[18]			X		X				

[1] Informed consent must be obtained prior to participation in any protocol-related activities that are not part of routine care.

[2] Initial evaluation of participant eligibility will be performed by Investigator.

[3] Medical history and current therapies (medications and non-medications).

[4] Symptom-directed physical examination.

[5] Vital signs will include blood pressure, pulse, respiration rate, and temperature. On treatment visits will be conducted three times a day, within 120 minutes before administration, within 1 hour after administration, and 4-6 hours after administration, respectively. On other visits will be conducted once during the visit.

[6] 12-lead ECG on treatment visits will be conducted three times a day, within 120 minutes before administration, within 1 hour after administration, and 4-6 hours after administration, respectively. On other visits will be conducted once during the visit.

[7] Spirometry assessments will be started 5 minutes after the dosing with frequent spirometry measurements at 5 (± 1 min), 15 (± 1 min), 30 (± 5 min) 60 (± 5 min) minutes. On other visits will be conducted once during the visit.

[8] Participant will be discharge from the clinic when all required assessments for V9 are performed.

[9] If hematology, biochemistry, coagulation and urinalysis are completed within 7 days prior to dosing, this assessment does not need to be repeated on Day-1.

[10] Hematology

Hemoglobin, Hematocrit (HCT), Red Blood Cells (RBC), White Blood Cells (WBC) with total and differential count, Absolute Neutrophil Count (ANC) and platelets.

[11] Biochemistry

Hepatic function indicators: total bilirubin, alkaline phosphatase, aspartate aminotransferase (AST), alanine aminotransferase (ALT), total protein, albumin Lactate dehydrogenase (LDH), amylase and lipase

Renal function indicators: Serum creatinine, eGFR

Electrolytes: sodium, potassium, chloride, calcium and bicarbonate

Other: glucose (random), triglyceride (TG), cholesterol (total), Creatine kinase.

[12] Coagulation

Prothrombin time (PT), activated partial thromboplastin time (APTT), thrombin time (TT), fibrinogen (FIB)

[13] Serum pregnancy test in screening visit (Will include FSH and estradiol levels at screening for post-menopausal women only) and EOT, and Urine pregnancy test in other visits.

[14] Urine samples will be tested for color, appearance, specific gravity, pH, protein, glucose, occult blood, ketones, leukocyte esterase, nitrite, bilirubin, and urobilinogen.

[15] Nasopharyngeal or nasal swab sample will be collected for COVID-19 antigen rapid test at screening and qRT-PCR test on Day -1, Day 9, Day 14 and Day 28.

[16] PK timepoints: Cohorts B1 to B2: Blood samples will be collected on Day 1 and Day 7 before dosing, and afterwards at 5 min (\pm 1 min), 15min (\pm 2 min), 0.5 h (\pm 5 min), 1 h (\pm 5 min), 2 h (\pm 5 min), 4 h (\pm 5 min), 8 h (\pm 10 min), 10 h (\pm 10 min) on Day 1; and at 5 min (\pm 1 min), 15min (\pm 2 min), 0.5 h (\pm 5 min), 1 h (\pm 5 min), 2 h (\pm 5 min), 4 h (\pm 5 min), 8 h (\pm 10 min), 10 h (\pm 10 min), 24 h (\pm 10 min) and 48 h (\pm 10 min) after dosing on Day 7; and before dosing on Day 2 to Day 6 (Total 25 samples).

[17] ADA timepoints: Blood samples will be collected on Day 1 before dosing, Day 14, and Day 28.

[18] IP administration: MAD cohorts B1-B2: MBS-COV treatment administration through a portable mesh nebulizer for 7 consecutive days, once daily, according to the cohort dosing schedule

[19] Adverse events and concomitant medications will be followed up on Day 28.

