2.2. STUDY OUTCOME MEASURES

2.2.1. Primary Outcome Measures

The primary outcome measures in this study are:

- Evaluation of the safety and tolerability of MBS-COV after a single and multiple dose administrations in healthy participants. The following parameters will be used to assess safety:
 - Incidence and severity of Treatment-Emergent Adverse Events (TEAEs)
 - Incidence of withdrawals due to Adverse Events (AEs)
 - Incidence of Treatment-Related Adverse Events
 - Incidence of Serious Adverse Events (SAEs)
 - Change/shifts in laboratory values from baseline
 - Change in vital signs including blood pressure, pulse, respiratory rate, and temperature from baseline
 - Change in spirometry from baseline to assess the acute bronchospasm
 - Change in other safety examination parameters from baseline

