4.2. PART A

4.2.1. Part A (SAD) - Screening Visit (SV: Up to 28 Days prior to Day 1):

The participant will sign and date the ICF, and screening visit procedures of Part A of the study are per below:

- Informed consent will be obtained prior to any study-related procedures
- Eligibility assessment per the inclusion and exclusion criteria
- Participant demographics
- Medical history
- Vital signs
- Height, Weight, BMI
- Physical examination
- 12-lead electrocardiogram (12-lead ECG)
- Chest X-ray
- List concomitant medications
- Spirometry assessment
- Laboratory assessments (hematology, chemistry, coagulation and urine analysis, urine drug screening and alcohol screen)
- Screening for infectious diseases (HIV antibody; HbsAg antigen; HCV antibody positive)
- Serum pregnancy test
- Nasopharyngeal or nasal swab for COVID-19

If spirometry, hematology, chemistry, coagulation, and urine analysis, are completed within 7 days prior to dosing, this assessment does not need to be repeated on Day-1.

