4.2.3. Part A (SAD) - Treatment Visit 1: Baseline Visit (T1: Day 1)

The first assigned study treatment dose will be administered after completion of all study evaluations. Adverse events and changes in concomitant medications will be collected. Participants in Cohorts A1 to A3 will be inhaled a single dose of MBS-COV or placebo through a portable nebulizer on Day 1.

The following assessments will be performed:

- Medical history (pre dose)
- Vital signs (pre and post dose) (Vital signs will include blood pressure, pulse, respiration rate, and temperature. On treatment visits will be conducted three times a day, within 120 minutes before administration, within 1 hour after administration, and 4-6 hours after administration, respectively.)
- Randomization (pre dose)
- Physical examination (pre and post dose)
- 12-lead ECG (pre and post dose) (12-lead ECG on treatment visits will be conducted three times a day, within 120 minutes before administration, within 1 hour after administration, and 4-6 hours after administration, respectively.)
- List concomitant medications
- PK timepoints: Cohorts A1 to A3: For the single dose on day 1, blood samples will be collected before dosing, and afterwards at 5 min (± 1 min), 15 min (± 2 min), 0.5 h (± 2 min), 1 h (± 5 min), 2 h (± 5 min), 4 h (± 5 min), 8 h (± 10 min), 10 h (± 10 min) after dosing.
- ADA timepoints: Blood samples will be collected on Day 1 before dosing
- Spirometry Assessment (Spirometry assessments will be started 5 minutes after the dosing with frequent spirometry measurements at 5 (± 1 min), 15 (± 1 min), 30 (± 5 min), 60 minutes (± 5 min).)

- Adverse events evaluation after first dose
- Participants will be confined till 24 hours pharmacokinetic samples are obtained following study drug administration.

4.2.4. Part A (SAD) – Treatment Visit 2 to Treatment Visit 5/End of Treatment (T2: Day 2 to T5: Day 7)

The following assessments will be performed (refer to the schedule of events Table 4-1)

- Vital signs
- Physical examination, including dermatologic examination
- 12-lead ECG
- List concomitant medications
- Laboratory assessments (hematology, chemistry, coagulation and urine analysis) (T2, T3, and T5 only)
- Chest X-ray (T5 only)
- PK timepoints: Cohorts A1 to A3: For the single dose on day 1, blood samples will be collected at 24 h (\pm 10 min) and 48h (\pm 10 min) after dosing.
- Serum pregnancy test only on T5 (EOT)
- Adverse events evaluation

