7.5. PHYSICAL EXAMINATION

The physical examination will include routine examinations for the following:

- Constitutional/General Appearance
- Head, Ears, Eyes, Nose, Throat (HEENT)
- Neurologic
- Chest (including heart and lung)
- Abdomen
- Musculoskeletal and Extremities
- Dermatologic
- Lymphatic
- Psychiatric

Each abnormality will be recorded and the Investigator will record an assessment of its clinical significance.

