7.11. SPIROMETRY ASSESSMENT

It is to be used as a validation method to ensure participants don’t have a former yet undiagnosed respiratory disease and to validate the presence of abnormal Forced Expiratory Volume1(FEV1) values.

Spirometry will evaluate the respiratory functions of acute bronchospasm. Spirometric parameter including FEV1% (the percent of predicted FEV1), FEV1/FVC, and peak expiratory flow (PEF).

Extra spirometry assessments may be repeated at the discretion of the investigator.

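### Spirometry change is a primary outcome for acute bronchospasm, but no dosing day has a scheduled pre-dose spirometry reading

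*Protocol*

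**What the plan says.** Protocol Section 2.2.1 lists among the primary outcome measures: "Change in spirometry from baseline to assess the acute bronchospasm". SAP Sections 4.1.1 and 4.2.1 repeat this for each part.

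**Dosing days.** Footnote 7 of Tables 4-1 and 4-2 reads "Spirometry assessments will be started 5 minutes after the dosing with frequent spirometry measurements at 5" and continues with 15, 30 and 60 minutes. Sections 4.2.3 (Part A Day 1), 4.3.3 (Part B Day 1) and 4.3.4 (Part B Days 2-7) give the same post-dose times and no others. In both schedule tables the Day 1 Pre-Rx cell for spirometry is blank.

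**Before dosing.** Spirometry is scheduled at screening and on Day -1. In Part A the Day -1 reading can be waived: "If spirometry is completed within 7 days prior to dosing, this assessment does not need to be repeated on Day-1". Section 4.2.1 repeats the waiver. For Part B, Section 4.3.2 includes spirometry in the waiver ("If spirometry, hematology, chemistry, coagulation, and urine analysis, are completed within 7 days prior to dosing"), but Table 4-2 footnote 7 contains no waiver.

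**Other measurements.** For ECG the rule is "12-lead ECG on treatment visits will be conducted three times a day, within 120 minutes before administration", followed by two post-dose readings. Vital signs follow the same pattern.

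**Analysis.** SAP Section 7.1 takes as baseline the last valid value before the first dose. SAP Section 7.4.7 summarises spirometry and its change from baseline for each visit, and lists all results by subject.

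**The concern.** Acute bronchospasm develops over minutes, so its natural reference is a reading taken shortly before the same dose. Here the reference comes from another day, and day-to-day variation enters every computed change in both arms.

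The exposed pattern is a moderate fall already present at 5 minutes and still present at 60. The post-dose series cannot show it as a change, because all four readings are low. No later scheduled reading shows recovery either: Part A schedules no spirometry after 60 minutes, and in Part B the next reading follows the next dose. With 2 placebo participants per cohort, the comparison arm gives little help in judging an individual value.

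Part B has a further difficulty. On Days 2-7, change from a pre-study baseline mixes any carry-over from earlier doses with the response to that day's dose.

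**Working it through.** The documents state no figure for this point, so there is none to reproduce. The check is a count from the schedule, followed by an illustration.

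**Inputs from the documents**
- Part A: 24 participants, 1 dosing day, 4 post-dose readings.
- Part B: 20 participants, 7 dosing days, 4 post-dose readings per day.
- Placebo (Section 8.4): 2 per cohort, so 3 × 2 = 6 in Part A and 2 × 2 = 4 in Part B. The SAP does not state whether these are pooled.

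**Scheduled pre-dose readings on dosing days, per participant**

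| | Spirometry | ECG | Vital signs |
|---|---|---|---|
| Part A | 0 | 1 | 1 |
| Part B | 0 | 7 | 7 |

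**Post-dose readings with a same-day pre-dose value**
- Total: 24 × 4 = 96 in Part A and 20 × 7 × 4 = 560 in Part B; 96 + 560 = 656.
- As planned: 0 of 656.
- With a Day 1 pre-dose reading: 96 + 20 × 4 = 176; 176/656 = 26.8%. In Part B this is 4 of 28 readings per participant (14.3%), leaving 20 × 24 = 480 without one.
- With pre-dose readings on Part B Days 2-7 as well: 656 of 656.

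**Age of the baseline**
- Day 1: 1 day by default, up to 7 days under the waiver.
- Part B Day 7: 1 + 6 = 7 days by default, up to 7 + 6 = 13 days if the waiver applies.
- A Day 1 pre-dose reading would make it 6 days on Part B Day 7.

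**Illustration of the added noise (all SDs assumed)**
Let w be the within-day SD and b the between-day SD of a reading.

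*One post-dose reading minus baseline.* The SD is √(2w²) with a same-day baseline and √(2w² + 2b²) with another day's baseline. The ratio is √(1 + (b/w)²).

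| b/w | SD ratio |
|---|---|
| 0.5 | 1.12 |
| 1 | 1.41 |
| 2.5 | 2.69 |

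*Mean of the four post-dose readings minus baseline*, which is closer to a sustained fall. The SD is √(w²/4 + w²) same-day and √(w²/4 + w² + 2b²) other-day. With w of 2-3% and b of 2-6% of baseline FEV1:
- SD: 2.2-3.4% same-day, 3.6-9.1% other-day; the ratio is about 1.3 to 3.9.
- Chance that noise alone gives a mean fall of 10% or more (an illustrative threshold): at most 0.14% same-day, 0.3% to 13.7% other-day.

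The two ratios differ because the quantities and assumed SDs differ. Neither model separates a 1-day-old from a 7-day-old baseline. They therefore show no cost of the waiver itself, and no gain on Part B Days 2-7 from a Day 1 reading alone.

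**The case against.** The strongest reply is that the gap matters little. The study is descriptive with no hypothesis test, and participants are healthy with normal spirometry. Four serial readings within an hour would show a brief fall and its recovery, and a large fall would stand out against any baseline. Without the waiver the Day 1 baseline is only one day old. Screening and Day -1 readings also give most participants a direct look at their own day-to-day variation. Section 7.11 adds: "Extra spirometry assessments may be repeated at the discretion of the investigator". Same-day pre-dose respiratory rate is recorded, and the Day 1 pre-dose physical examination covers the lungs. All of this stands, and it keeps the point from being more serious. None of it gives every participant a same-day pre-dose spirometry value. The general instruction to dose on Day 1 after completing evaluations does not schedule one either.

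A second reply is that the waiver is not the cause: deleting it would leave the count at 0 of 656. That is correct. The cause is the post-dose-only schedule; the waiver only lets the baseline be older.

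A third is that the SD ratios rest on assumed values. That is also correct. Only their direction is supported.

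A fourth is that moving the Day -1 test to Day 1 would weaken the eligibility check made at admission. This is a fair cost, and adding a reading instead of moving one avoids it.

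**Conclusion.** The point holds. A named primary safety outcome about a change over minutes has no scheduled same-day reference on any dosing day in either part, although ECG and vital signs have one. The schedule tables, footnotes and visit text agree on this.

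The effect is loss of precision, with no bias claimed, and it chiefly concerns moderate falls that persist through 60 minutes. The counts assume full enrolment and complete attendance. The size of the loss cannot be settled from the documents. The change is worth making because it is cheap; the trial remains interpretable without it. The disagreement between Section 4.3.2 and Table 4-2 footnote 7 is a separate, definite inconsistency.

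**What to change.** **Step 1, both parts.** Schedule baseline spirometry on Day 1 before dosing, in the 120-minute window already used for ECG and vital signs, and state that the 7-day waiver does not replace it. Either move the Day -1 reading or add a new one:
- Moving leaves eligibility resting on screening spirometry, which inclusion criterion 5 already accepts, so that criterion can stay as it is. Participants who would have used the waiver have one extra test.
- Adding keeps the Day -1 check and costs at most 44 extra tests.

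In SAP Section 7.4.7, summarise change from the Day 1 pre-dose value at each post-dose time point, and each participant's worst post-dose change.

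**Step 2, Part B.** Take one brief pre-dose reading on each of Days 2-7, while participants are confined, and also report change from that same-day value. This costs 6 readings per participant, 6 × 20 = 120 in total.

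**Separately,** reconcile Section 4.3.2 with Table 4-2 footnote 7 on the Part B waiver.

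Step 1 needs a protocol amendment (both schedule tables with footnote 7, the Day -1 and Day 1 visit lists, and the waiver sentences in Sections 4.2.1 and 4.3.2) and the SAP wording. Step 2 also changes Section 4.3.4. At the site, each reading takes a few minutes before dosing.
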